SpO ₂	Oxygen saturation by pulse oximetry
WBC	White blood cell
WHO	World Health Organization

1 INTRODUCTION

This statistical analysis plan (SAP) is to provide details on the planned statistical methodology for analysis of the study data, and outlines the statistical programming specifications for the tables, listings and figures. It describes the data collected and the planned analysis to assess safety and efficacy as well as the anticipated data transformations and manipulations, and other details of the analyses not provided in the study protocol.

This SAP is based on BVD-CNV2_IT Protocol_A2 dated on 02Sep2014 and CRFv 5.0 dated on 17Jan2017 .

2 Study Objectives

- To determine the safety profile, dose limiting toxicities (DLT), and maximum tolerated dose (MTD) of *Clostridium novyi*–NT (*C. novyi*-NT) in humans with treatment-refractory solid tumor malignancies when administered as a single intratumoral (IT) injection.
- To document preliminary anti-tumor activity of both the injected tumor and an overall response after administering a single IT injection of *C. novyi*-NT in humans with treatment-refractory solid tumor malignancies. The evaluation of anti-tumor activity will include: 1) a response for the injected tumor and, 2) an overall response.
- To study the presence of circulating *C. novyi*-NT spores after administration as a single IT injection to humans with treatment-refractory solid tumor malignancies.
- To measure the host immune and inflammatory response to *C. novyi*-NT administered as a single IT injection in humans with treatment-refractory solid tumor malignancies.

3 Investigational Plan

3.1 General Considerations - Summary of Study Design

Patients who provide informed consent will be screened within 21 days prior to *C. novyi*-NT spore administration. Patients will report to the clinical site within 24 hours of Day 0 to reconfirm eligibility and for baseline assessments. Eligible patients will be admitted and enrolled sequentially into a dosing cohort as described in the section 3.6 of this SAP.

Spore dose administration will occur on Day 0, and patients will remain in-house for observation through Day 7 (a total of 8 days). Patients will return to the clinical site for follow-up visits at the following time points: Days 11, 14 (Week 2), 18, 21 (Week 3), 25, 28 (Week 4) and 2, 4, 8, and 12 months post-dose. Assessment of safety, efficacy, and

disposition of *C. novyi*-NT will be performed at scheduled time points throughout the study.

A standard "3+3" dose escalation will be used. The following definitions and rules will be employed:

- Toxicity Criteria will be those listed in the National Cancer Institute (NCI) Common Terminology Criteria for Adverse Events (CTCAE), Version 4.0, which is available at http://ctep.cancer.gov/reporting/ctc.html
- An adverse event (AE) of Grade 3 toxicity lasting three (3) days or longer or Grade 4 toxicity of any duration that is assessed to be at least possibly related to study agent will be considered a DLT. Signs and symptoms of *C. novyi*-NT infection which are associated with a Sequential Organ Failure Assessment (SOFA) score > 5 that require invasive intervention including percutaneous drainage of an abscess or that result in prolonged hospitalization (> 5 days) will also qualify as DLTs.
- DLT assessment period is defined as 4 weeks after dosing of the last patient in a cohort.
- Toxicity will be assessed from administration of study agent up to 8 weeks.
- The dose escalation rules, as outlined in Table 1, will be applied.
- Additional patients will be enrolled at the MTD to achieve a total of six patients at that dose level if fewer than six patients were treated previously at that dose.
- Doses will be increased in successive cohorts until the MTD is reached or until complete germination and tumor regression occurs, making higher doses unnecessary.
- The MTD (or dose at which complete germination and tumor regression occurs) will be the recommended dose for future Phase II *C. novyi*-NT IT administration studies.

Number of Patients with DLT at a Given Dose Level	Escalation Decision Rule	
0 out of 3	The dose escalation will proceed. Three patients will be enrolled at the next dose level	
1 out of 3	 Three more patients will be enrolled at this dose level If zero of three patients experience a DLT, then dose escalation will proceed to the next dose level. If one or more patients suffer a DLT, then dose escalation will stop. This dose will be the maximally administered dose (i.e., the minimum intolerated dose). Three additional patients will be entered at the next lowest dose level (i.e., the MTD) if only three patients were treated previously at that dose. 	
≥ 2	Dose escalation will be stopped. This dose level will be declared the maximally administered dose (i.e., the minimum intolerated dose). Three additional patients will be entered at the next lowest dose level (i.e., the MTD) if only three patients were treated previously at that	

Table 1: Dose Escalation Decision Rules

BioMed Valley Discoveries

dose.

Patients will be monitored for infectious complications or other treatment – emergent adverse events with the objective of deciding if and when to initiate antibiotics and/or additional interventions. Patients will be followed with serial imaging studies for therapeutic response. The first patient in a cohort will be observed for a minimum of 2 weeks before treating the next patient, while there will be no required minimum observation interval before subsequent patients in the same cohort can be dosed. Patients will be observed for a minimum 4-week interval between cohorts. The planned follow-up period for every patient who receives *C. novyi*-NT will be 1 year.

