4.5 Safety Evaluation

4.5.1 Adverse Events (AEs)

Adverse Events will be mapped to the Medical Dictionary Regulatory Activities (MedDRA), Version 14.1 with the lowest level term that most accurately reflects the adverse event.

Adverse events will be categorized as:

- Treatment emergent adverse event (TEAE): A treatment-emergent adverse event is defined as any event not present prior to the initiation of the treatments or any event already present that worsens in either intensity or frequency following exposure to the treatments.
- Non-treatment emergent adverse events (NTEAE): An AE that occurred before the first administration of IMP and did not worsen in severity or frequency after IMP exposure.

All adverse event data recorded on the eCRFs will be listed by dose level and patient. Included on the AE listing will be the adverse event, start date and time, outcome, stop date and time, CTCAE grade, relationship to study drug, action taken, whether the AE was serious, whether TEAE, whether or not a concomitant medication was taken, time of AE onset relative to IMP dosing and AE duration.

All serious adverse events will be listed. A listing of all AEs leading to treatment discontinuation will be presented. Details of death and hospitalization relating to serious adverse events will be listed.

As defined in the protocol, all adverse events will be assigned a CTCAE grade of 1 to 5.

Unless specified otherwise, all adverse event summaries will include the TEAEs only. In these summaries the count of AEs will be the number of patients reporting adverse events and not the number of events reported. If the same AE (preferred term) is reported several times for the same patient, it will only appear once for that specified dose level in the summary tables. For patients with multiple adverse events of the same preferred term and of different intensity, the highest intensity assessment will be used in summaries presented by intensity.

For purposes of the summary tables, AEs will be classified as either being related to IMP or not related. AEs related to IMP will include AEs classified as 'Definite', 'Probable', or 'Possible'. AEs not related to IMP will include AEs classified as 'Not Related' or 'Unlikely'.

Frequency counts will be categorized and displayed by the MedDRA system organ class and preferred term.

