An overview table will be presented by dose level and overall. This summary will present the number and percentage of patients, as well as number of events with treatment emergent: AEs; SAEs; AEs related to IMP; SAEs related to IMP; AEs leading to discontinuation of IMP; AEs by CTC Grade; and AEs with CTC Grade 3 or higher.

Other summary tables for adverse events will include:

- 1) Number and Percentage of Subjects with Treatment Emergent Adverse Events by System Organ Class, Preferred Term, and Dose Level
- 2) Number and Percentage of Subjects with Treatment Emergent Adverse Events 'Related to IMP' by System Organ Class, Preferred Term, and Dose Level
- 3) Number and Percentage of Subjects With Serious Treatment Emergent Adverse Events by System Organ Class, Preferred Term, and Dose Level
- 4) Number and Percentage of Subjects With Serious Treatment Emergent Adverse Events 'Related to IMP' by System Organ Class, Preferred Term, and Dose Level
- 5) Number and Percentage of Subjects with Treatment Emergent Adverse Events 'Related to IMP' by System Organ Class, Preferred Term, CTCAE Grade, and Dose Level
- 6) Number and Percentage of Subjects with Treatment Emergent Adverse Events 'Not Related to IMP' by System Organ Class, Preferred Term, CTCAE Grade, and Dose Level
- 7) Number and Percentage of Subjects with Treatment Emergent Adverse Events with Frequency >=2 Patients by Preferred Term
- 8) Number and Percentage of Subjects With Serious Treatment Emergent Adverse Events by Preferred Term

Above tables 1) - 4) present columns of Any grade and Grade ≥ 3 for each dose level, any grade includes missing grade; tables 5) and 6) present each available grade at each dose level; tables 7) and 8) present number of patients and number of events at each dose level by descending frequency of overall dose.

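### The DLT definition in SAP section 3.1 stops at Grade 4, so a related event recorded only as Grade 5 and outside the infection criterion is, read literally, not a DLT

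*SAP*

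**What the plan says.** SAP section 3.1 gives two routes to a DLT.

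- **Grade route:** "Grade 3 toxicity lasting three (3) days or longer or Grade 4 toxicity of any duration", judged at least possibly related to the study agent.
- **Infection route, with no grade condition:** signs and symptoms of *C. novyi*-NT infection with a SOFA score above 5 that either need an invasive intervention or prolong the hospital stay by more than 5 days.

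Section 4.5.1 sets the grading scale: "As defined in the protocol, all adverse events will be assigned a CTCAE grade of 1 to 5". The overview table in the same section uses an open range: "AEs with CTC Grade 3 or higher".

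Table 1 in section 3.1 turns DLT counts into decisions. At 0 of 3: "The dose escalation will proceed. Three patients will be enrolled at the next dose level". At 1 of 3, three more patients are enrolled, and then: "If zero of three patients experience a DLT, then dose escalation will proceed to the next dose level". One or more DLTs in the second three, or two or more at the dose level, stop escalation. Section 6.1 lists Table 14.3.6, the summary of DLTs by CTCAE grade.

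**The concern.** The grade route is a closed list of two grades. Grade 5 is a separate recorded grade in this SAP, and the SAP writes an open range elsewhere when it means one. Nothing else in the SAP makes a related death a DLT. Taken at its word, the definition therefore leaves out the most severe outcome on the scale.

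Determining the DLTs and the maximum tolerated dose (MTD) is part of the first objective in section 2. Table 1 decides on counts of 0, 1 or 2 patients, so one uncounted event shifts the decision by a full step, always towards escalation.

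**Working it through.** The SAP states no operating characteristic for the 3+3 rule, so there is no figure to reproduce. The check is a reading of the text, followed by its consequence under Table 1.

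**Step 1. Which related deaths fall through?** A related fatal event is still a DLT if any of these holds:

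- it was also recorded at Grade 4 before death;
- it was also recorded at Grade 3 for 3 days or longer;
- it meets the infection route.

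What remains is a related event recorded only as Grade 5 and outside the infection route. Examples are a sudden death, a fatal bleed, or a rapid septic death with neither an invasive intervention nor a prolonged stay.

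**Step 2. Decisions under Table 1, given that such a death has occurred.** Let p be the DLT risk of each remaining patient (an assumption; the SAP gives none). The chance that the second three patients have no DLT is (1 − p)³:

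- p = 10%: 0.9³ = 0.729
- p = 20%: 0.8³ = 0.512
- p = 30%: 0.7³ = 0.343

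| Situation | Literal count and action | Count with Grade 5 included |
|---|---|---|
| One such death in the first three, no other DLT | 0 of 3: escalate, chance 1 | 1 of 3: enrol three more; chance of escalating 0.73, 0.51 or 0.34 at p = 10%, 20% or 30% |
| One such death plus one other DLT in the first three | 1 of 3: enrol three more; chance of escalating 0.51 at p = 20% | 2 of 3: stop |
| One such death and no other DLT in the second three, after 1 of 3 | 0 of the second 3: escalate | At least 1: stop |

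These figures are conditional on the death and on everyone applying the rule literally. They are not operating characteristics of the design.

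**Step 3. Unconditional illustration.** For a per-patient DLT risk p, the chance of escalating past a dose is

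(1 − p)³ + 3p(1 − p)² × (1 − p)³.

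At p = 20% this is 0.512 + 0.384 × 0.512 = 0.709. Suppose the true risk is 20% and g percentage points of it are Grade-5-only events that the literal rule does not count. The rule then works with 20% − g:

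- g = 2 points (p = 18%): 0.752
- g = 5 points (p = 15%): 0.814

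At a true risk of 33%, the chance is 0.434 with Grade 5 counted, and 0.474 or 0.536 for g = 2 or 5. Both the risks and g are assumptions. For a small g, the effect on the design as a whole is modest.

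**Step 4. Reporting.** Sections 4.1.4 and 4.5.1 give no separate derivation of a DLT. Section 3.1 is therefore the only definition in the SAP from which Table 14.3.6 can be built, and under it the death in Step 2 would not appear there.

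**The case against.** **The rule belongs to the protocol.** Section 3.1 summarises the design, and escalation runs under the protocol, which was not at hand and may cover death. This stands as a limit: the SAP text cannot show that the protocol has the same gap. It does not make the SAP wording right.

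**The gap is narrow and would be overridden.** This also stands. The case needs a related death with no qualifying earlier grade, outside the infection route, and a team that follows the words over clinical sense.

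**Timing.** The revision history in section 5 dates the addition of Cohort 6 to 27 February 2017 and the last revision to 17 March 2017. An edit to this SAP would mainly affect the DLT table and the MTD statement, and would hardly steer dosing. This stands.

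**Table 14.3.6 might rest on an investigator or sponsor designation, and the death would be visible elsewhere.** The SAP describes no such designation. Related deaths would indeed appear in Tables 14.3.5 and 14.3.7 and in Listing 16.2.7.1, so the event would not be hidden. It would only be missing from the table that supports the MTD.

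**A second defect that a reader might infer: the DLT window.** The SAP says "DLT assessment period is defined as 4 weeks after dosing of the last patient in a cohort", and also "The first patient in a cohort will be observed for a minimum of 2 weeks before treating the next patient". The first patient is thus followed for at least 2 + 4 = 6 weeks and the last for 4. The documents do not support calling this an error. The line reads naturally as the timing of the cohort decision, every patient has at least 4 weeks, and the extra time for earlier patients is cautious. Nor are early events in the first patient lost: "Toxicity will be assessed from administration of study agent up to 8 weeks". A window limited to each patient's own first 28 days would drop known late events from the decision, which is a trade-off and not a correction.

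**Conclusion.** The point holds as a wording error. The grade route omits Grade 5, and a related event recorded only at that grade and outside the infection route is literally not a DLT. One such death among the first three, with no other DLT, moves the decision from expanding the cohort to escalating, and a Table 14.3.6 derived from the definition omits it.

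The size is small in expectation because the case is rare and would probably be overridden. It still merits correction because the rule is safety-critical and the error always favours escalation. The conclusion rests on the SAP text alone; the probabilities rest on assumed DLT risks.

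Two stronger readings go too far. A reader might infer that related deaths in general escape the definition, but deaths with a qualifying earlier grade or meeting the infection route are counted. A reader might also infer that doses were escalated wrongly, but nothing in the SAP shows that such a death occurred or that the rule was applied literally.

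**What to change.** In the grade route of the DLT definition in section 3.1, insert *or higher (including Grade 5)* after Grade 4, and leave the 3-day condition on Grade 3 unchanged. State in section 4.5.1 that Table 14.3.6 is derived from the amended definition. Compare the wording with the protocol, and if the protocol has the same closed list, clarify it there too. Leave the DLT assessment period as it is.

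The cost is a few words in one sentence and one added line. Grades 1 to 5 and the relation to study agent are already recorded, so no new assessment or data collection is needed.

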3.2 Study Endpoints

Safety

- Changes from the pre-study physical examination findings
- Vital signs measurements (blood pressure, heart rate, oral temperature, and respiratory rate, body weight)
- Oxygen saturation by pulse oximetry (SpO2)
- Sequential Organ Failure Assessment (SOFA) score
- Eastern Cooperative Oncology Group (ECOG) Performance Grade assessments
- Laboratory assessments (Complete Blood Count (CBC) with differential, serum chemistry, coagulation, C-reactive protein (CRP), cultures from blood, and when available, tumor biopsy and abscess samples) at baseline and throughout the study period and changes from baseline
- CT/MRI imaging as scheduled on Day 7 and unscheduled imaging to investigate the possibility of abscess formation or to explore the unexpected toxicity
- Adverse events and Serious AE (SAE) count and rate, including symptoms of infection
- Antibiotic use (name, route, initiation date, and whether based on temperature or investigator's judgment or as per mandated in the protocol)
- Use of concomitant medications throughout the study period
- Telephone contact and survival information

Efficacy

- Tumor size of the targeted injection lesion and other targeted metastatic lesions, measured by Computed Tomography (CT) scans or Magnetic Resonance Imaging (MRI) scans
- Response Evaluation Criteria in Solid Tumors (RECIST) assessment on the injection lesion
- Overall RECIST response

Pharmacodynamics

- Serum banking to assess immune response: C-Reactive Protein (CRP), whole blood and serum samples, pre-dose injected tumor sample, post-dose injected and non-injected tumor samples, abscess material, and selected cytokines as markers of systemic inflammation
- Blood cultures, abscess material, and post-dose injected and non-injected tumor samples (when available) for detection of presence or absence of *C. novyi*-NT.

3.3 Interim Analysis

No interim analysis is planned.

3.4 Study Population

The study population is patients with solid tumor malignancies that are refractory to standard therapy or without available standard therapy. Men and women of all races and ethnic groups are eligible for this trial. Eligible patients must meet all the inclusion criteria and none of the exclusion criteria as stated in the protocol.

3.5 Sample size

Three to six (3 to 6) patients per cohort will be enrolled until the MTD is reached or until complete germination and tumor regression occurs.

3.6 Treatment Assignment

Patients will receive treatment with *C. novyi*-NT at a dose corresponding to their assigned cohort, starting with Cohort 1. The initial planned dosing groups are summarized Table 2 below. Based on initial patient tolerability findings and reported toxicities experienced during the study, higher dosing groups will be incorporated. *C. novyi*-NT spores will be administered as an IT injection into the target lesion. Patients will be given IV hydration after dosing.

Cohort	Number of Patients	Dose (x 10 ⁴ spores)
1	3 to 6	1
2	3 to 6	3
3	3 to 6	10
4	3 to 6	30
5	3 to 6	100
6	3 to 6	300

3.7 Blinding

Not applicable. Patients will be enrolled sequentially into a given dosing cohort.

3.8 Eligibility Evaluation and Baseline Characteristics

3.8.1 Informed Consent

Each patient's informed consent will be taken at screening.

Separate consent will be requested to obtain/retain (for genetic and/or not genetic testing) of blood, serum, abscess material, archived tumor tissue and biopsy samples (when available). In addition, a separate consent for photograph collection from injected tumor and the storage for future use of information/data resulting from analysis of patient's samples will be requested.

3.8.2 Inclusion/Exclusion

Patient eligibility will be assessed at screening.

3.8.3 Blood Type

At Day -1 to Day 0 pre-dose patient blood type will be recorded.

3.8.4 Pregnancy Test

In female patients, with childbearing potential, serum pregnancy testing will be performed at screening and Day -1 to Day 0 pre-dose.

3.8.5 Demographics and Medical History

Medical history information will be collected at screening and Day -1 to Day 0 pre-dose.

Demographic information will be collected at screening.

The following demographic information will be recorded:

- Derived age at screening
- Sex (male or female)
- Race (American Indian or Alaska Native, White, Black, Asian, Native Hawaiian or Other Pacific Islander, Other with specified)
- Ethnicity (Hispanic/Latino, Not Hispanic/Latino, Other with specified)

3.8.6 Brain MRI

A brain MRI will be conducted at screening to evaluate for metastatic disease.

3.8.7 Echocardiogram (ECHO)

An echocardiogram will be performed at screening.

3.8.8 12-Lead Electrocardiograms (ECG)

12-lead ECGs will be performed at screening and Day -1 to Day 0 pre-dose. Information collected will include date and actual time of assessment, whether ECG was normal, and the recorded values of Bazett (QTcB) msec, Fridericia (QTcF) msec, RR (msec), PR (msec), QRS (msec) and HR.

3.8.9 Prior Cancer History

Prior cancer history will be captured on the eCRF including information on:

- Diagnosis: date of initial diagnosis, histology, primary site at diagnosis, initial staging (tumor size, lymph nodes, metastatic), date of initial diagnosis of metastatic, current extent of disease.
- Diagnostic and therapeutic procedures: date of procedure, purpose of the procedure, and any findings.
- Prior Systemic Anticancer Therapy: regimen number, drug, intent, start and stop date, dose amount, unit, number of cycles, frequency of cycles, best response, reason for discontinuation, date of progression.
- Prior Cancer Radiotherapy: regimen number, location, field of treatment, intent, date of first and last fraction, total dose, and best response.

3.9 Safety Assessments

3.9.1 Adverse Events

An Adverse Event (AE) is any new untoward medical occurrence or worsening of a preexisting medical condition in a clinical investigation subject administered an investigational medicinal product, even if it does not have a causal relationship with that product. Any unfavorable or unintended sign, symptom, or disease temporally associated with the use of the study agent, whether or not it is considered study agent-related will be considered an AE. This includes any newly occurring event or previous condition that has increased in severity or frequency since the administration of the study agent.

Monitoring for AEs will occur from the time of informed consent until the patient completes the study. The post-dosing observation period will begin with an 8-day inpatient stay (Days 0 to 7). This inpatient stay can be extended and requires that at least 2 days elapse from the resolution of any signs of infection or serious AEs (SAEs) before discharge.

All Grade 3 and 4 clinical laboratory results that represent an increase in severity from baseline will be reported as AEs. A Grade 1 or 2 clinical laboratory abnormality should be reported as an AE only if it is considered clinically significant by the investigator.

All AEs, including observed or volunteered problems, complaints, or symptoms from the time of informed consent until 8 weeks post-dose are to be recorded, regardless of causality. After 8 weeks post-dose, only AEs with possible, probable, or definite relationship to the study agent will be reported with follow up as noted above for AEs within the first 8 weeks post treatment.

Adverse events will be evaluated against the baseline history and physical examination and intensity graded using the NCI CTCAE, Version 4.0, which can be accessed at http://ctep.cancer.gov/reporting/ctc.html.

All AEs experienced by a patient, irrespective of the suspected causality, will be monitored until the event has resolved or stabilized, until any abnormal laboratory values have returned to baseline or stabilized at a level acceptable to the PI or local investigator and Medical Monitor, until there is a satisfactory explanation for the changes observed, or until the patient is lost to follow-up.

A Serious Adverse Event (SAE) is any AE, occurring at any dose and regardless of causality that:

• Results in death.

• Is life-threatening. Life-threatening means that the patient is at immediate risk of death from the reaction as it occurs; it does not include a reaction which hypothetically might cause death had it occurred in a more severe form.

• Requires inpatient hospitalization or prolongation of pre-existing hospitalization except when an extended inpatient hospitalization is required to manage local tumor inflammation or abscessation in the injected tumor lesion site. This does not include scheduled admissions for study-related issues (e.g., inpatient IT injection of study agent).

• Results in persistent or significant disability/incapacity. Disability is defined as a substantial disruption of a person's ability to conduct normal life functions.

• Is a congenital anomaly/birth defect.

• Is an important medical event. An important medical event is an event that may not result in death, be life-threatening, or require hospitalization, but may be considered an SAE when, based upon appropriate medical judgment, may jeopardize the patient and may require an intervention (medical or surgical) to prevent one of the outcomes listed above as a definition of SAE (e.g., bronchospasms).

All SAEs will be recorded from signing of informed consent until 8 weeks after study agent administration. After 8 weeks post-dose, only SAEs with possible, probable, or definite relationship to the study agent will be reported.

